8.1.4 Dermatology life quality index

The DLQI is a PRO developed to measure dermatology-specific HRQoL in adult patients ([27](#)). The instrument comprises 10 items assessing the impact of skin disease on patients' HRQoL over the previous week. The items cover symptoms, leisure activities, work/school or holiday time, personal relationships including intimate, the side effects of treatment, and emotional reactions to having a skin disease. It is a validated questionnaire used in clinical practice and clinical trials ([26](#)). Response scale is a 4-point Likert scale (0 = "not at all" and 3 = "very much") for nine items. The remaining one item about work/studying asks whether work/study has been prevented and then (if "No") to what degree the skin condition has been a problem at work/study; the item is rated on a 3-point Likert scale ("Not at all" to "A lot"). Overall scoring ranges from 0 to 30, with a high score indicative of a poor HRQoL.

Participants will complete the questionnaire at time points according to SoA (see [Section 1.3](#)). The assessment tool is provided in [Section 10.7.4](#).

8.1.5 Pain and sleep numeric rating scales

Participants will be asked to rate their worst skin pain in the past 24 hours using a 0 to 10 NRS, with 0 = No pain to 10 = Worst pain possible.

In addition, participants will be asked to rate their sleep quality on their past night upon awakening, using a 0 to 10 NRS, with 0 = Worst possible sleep and 10 = Best possible sleep.

Participants will complete the skin pain NRS and sleep quality NRS once a day.

The assessment tools are provided in [Section 10.7.7](#) and [Section 10.7.8](#).

8.1.6 Hospital anxiety and depression scale

The HADS is a PRO instrument for screening anxiety and depression in non-psychiatric populations; repeated administration also provides information about changes to a patient's emotional state ([28, 29](#)). The HADS consists of 14 items, 7 each for anxiety and depression symptoms; possible scores range from 0 to 21 for each subscale. The following cut-off scores are recommended for both subscales:

- 0 to 7: normal
- 8 to 10: borderline abnormal (borderline case)
- 11 to 21: abnormal

Participants will complete the questionnaire as described in the SoA (see [Section 1.3](#)). The assessment tool is provided in [Section 10.7.5](#).

8.1.7 Patient Global Impression of Change of disease and Patient Global Impression of Severity

The PGIC is a one-item questionnaire that asks patients to provide the overall self-assessment of change in their PN overall on a 7-point scale, compared to just before patient started taking the study injection. Response choices are: 0 = “Very much better”, 1 = “Moderately better”, 2 = “A little better”, 3 = “No change”, 4 = “A little worse”, 5 = “Moderately worse”, 6 = “Very much worse”.

The PGIS is a one-item questionnaire that asks patients to provide the overall self-assessment of their disease severity on a 4-point scale for the past week. Response choices are: 1 = “none”, 2 = “Mild”, 3 = “Moderate”, 4 = “Severe”.

Participants will complete the 2 items as described in the SoA (see [Section 1.3](#)). The items are provided in [Section 10.7.9](#) and [Section 10.7.10](#).

8.1.8 Euroqol 5 dimensions questionnaire

The Euroqol-5 dimensions (EQ-5D) is a standardized PRO measure of health status developed by the EuroQOL Group in order to provide a simple, generic measure of health for clinical and economic appraisal ([30](#)). The EQ-5D consists of 2 parts: the descriptive system and the EQ visual analog scale (VAS). The EQ-5D descriptive system comprises the following 5 dimensions: mobility, self-care, usual activities, pain/discomfort, and anxiety/depression. Each dimension has 5 levels of perceived problems: “no problem”, “slight problems”, “moderate problems”, “severe problems” and “inability to do the activity”. The respondent is asked to indicate his/her health state by ticking (or placing a cross) in the box against the most appropriate statement in each of the 5 dimensions; this results in a 1-digit number expressing the level for that dimension. The digits for 5 dimensions can be combined in a 5-digit number describing the respondent’s health state. The EQ VAS records the respondent’s self-rated health on a vertical VAS where the endpoints are labeled “best imaginable health state (100)” and “worst imaginable health state (0)”. This information can be used as a quantitative measure of health outcome as judged by the individual respondents.

Participants will complete the questionnaire as described in the SoA (see [Section 1.3](#)). The assessment tool is provided in [Section 10.7.6](#).

8.1.9 Missed school/work days

Participants who are employed or enrolled in school will be asked to report the number of sick leave/missed school days since the last study assessment.

Participants will complete the questionnaire as described in the SoA (see [Section 1.3](#)). The assessment tool is provided in [Section 10.7.11](#).

8.1.10 Photography

Participants in selected sites who decide to participate in this substudy need to provide separate consent as described in the SoA (see [Section 1.3](#)). One or several lesions will be photographed at baseline. The same lesions will be photographed at subsequent visits to evaluate their progression. The detailed information will be provided in the photography user guide.

8.2 SAFETY ASSESSMENTS

Planned time points for all safety assessments are provided in the SoA (see [Section 1.3](#)).

8.2.1 Physical examinations

- A complete physical examination will include, at a minimum, assessments of the skin (full body skin exam), nasal cavities, eyes, ears, respiratory, cardiovascular, gastrointestinal, neurological, lymphatic, and musculoskeletal systems.
- Participants must be disrobed and provided with a hospital gown before the skin examination.
- Investigators should pay special attention to clinical signs related to previous serious illnesses.
- Any new finding or worsening of previous finding should be reported as a new AE.

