If a clinically significant finding is identified (including, but not limited to changes from baseline in QT interval corrected using Fridericia's formula [QTcF] after enrollment), the Investigator or qualified designee will determine if the participant can continue in the study and if any change in participant management is needed. This review of the ECG printed at the time of collection must be documented. Any new clinically relevant finding should be reported as an AE.

Any abnormal laboratory value or ECG parameter will be immediately rechecked for confirmation within a reasonable timeframe as assessed by the Investigator before making a decision of definitive discontinuation of the IMP for the concerned participant.

Handling of participants after definitive intervention discontinuation

Participants will be followed-up according to the study procedures specified in this protocol up to the scheduled date of study completion, or up to recovery or stabilization of any AE to be followed-up as specified in this protocol, whichever comes last.

Participants who discontinue the study intervention prematurely (prior to completing the 24-week treatment period) will perform, as soon as possible, the early termination visit with all assessments normally planned for the EOT Visit (Visit 6), to assure a complete clinical assessment in close temporal proximity to the premature termination of study treatment is available.

In addition, and to allow assessment of participant outcomes over the stipulated study period, patients will be asked and encouraged to complete all remaining study treatment visits, and participate in all assessments according to the visit schedule with a ± 3 day window. Under exceptional circumstances when a participant cannot come to the site for a scheduled visit, a phone contact can be made. During the phone contact, at least information about AEs, concomitant medication and status of PN should be collected.

All cases of definitive intervention discontinuation must be recorded by the Investigator in the appropriate pages of the eCRF when considered as confirmed.

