8.2.4 Clinical safety laboratory assessments

- See Appendix 2 ([Section 10.2](#)) for the list of clinical laboratory tests to be performed and to the SoA (see [Section 1.3](#)) for the timing and frequency.

- The Investigator must review the laboratory report, document this review, and record any clinically relevant changes occurring during the study in the AE section of the CRF. The laboratory reports must be filed with the source documents. Clinically significant abnormal laboratory findings are those which are not associated with the underlying disease, unless judged by the Investigator to be more severe than expected for the participant's condition.
- All laboratory tests with values considered clinically significantly abnormal during participation in the study or within 12 weeks after the last dose of study intervention should be repeated until the values return to normal or baseline or are no longer considered clinically significant by the Investigator or medical monitor.
 - If such values do not return to normal/baseline within a period of time judged reasonable by the Investigator, the etiology should be identified and the Sponsor notified,
 - All protocol-required laboratory assessments, as defined in Appendix 2 ([Section 10.2](#)), must be conducted in accordance with the laboratory manual and the SoA (see [Section 1.3](#)),
 - If laboratory values from non-protocol specified laboratory assessments performed at the institution's local laboratory require a change in participant management or are considered clinically significant by the Investigator (eg, SAE or AE or dose modification), then the results must be recorded in the CRF.

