 - An overdose (accidental or intentional) with the IMP is an event suspected by the Investigator or spontaneously notified by the participant and defined as at least twice the intended dose during an interval of less than 11 days. The circumstances (ie, accidental or intentional) should be clearly specified in the verbatim and symptoms, if any, entered on separate AE forms.
 - An overdose (accidental or intentional) with any NIMP is an event suspected by the Investigator or spontaneously notified by the participant and defined as at least twice the maximum prescribed daily dose, within the intended therapeutic interval. The circumstances (ie, accidental or intentional) should be clearly specified in the overdose form.

The definitions of an AE or SAE can be found in Appendix 3 ([Section 10.3](#)).

Adverse events will be reported by the participant (or, when appropriate, by a caregiver, surrogate, or the participant's legally authorized representative).

The Investigator and any qualified designees are responsible for detecting, documenting, and recording events that meet the definition of an AE or SAE and remain responsible for following up AEs that are serious, considered related to the study intervention or study procedures, or that caused the participant to discontinue the study intervention (see [Section 7](#)).

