- An AE is any untoward medical occurrence in a patient or clinical study participant, temporally associated with the use of study intervention, whether or not considered related to the study intervention.

NOTE: An AE can therefore be any unfavorable and unintended sign (including an abnormal laboratory finding), symptom, or disease (new or exacerbated) temporally associated with the use of study intervention.

Events meeting the AE definition

- Any abnormal laboratory test results (hematology, clinical chemistry, or urinalysis) or other safety assessments (eg, ECG, radiological scans, vital signs measurements), including those that worsen from baseline, considered clinically significant in the medical and scientific judgment of the Investigator (ie, not related to progression of underlying disease).
- Exacerbation of a chronic or intermittent pre-existing condition including either an increase in frequency and/or intensity of the condition.
- New conditions detected or diagnosed after study intervention administration even though it may have been present before the start of the study.
- Signs, symptoms, or the clinical sequelae of a suspected drug-drug interaction.
- Signs, symptoms, or the clinical sequelae of a suspected overdose of either study intervention or a concomitant medication.
- “Lack of efficacy” or “failure of expected pharmacological action” per se will not be reported as an AE or SAE. Such instances will be captured in the efficacy assessments. However, the signs, symptoms, and/or clinical sequelae resulting from lack of efficacy will be reported as AE or SAE if they fulfil the definition of an AE or SAE.

Events NOT meeting the AE definition

- Any clinically significant abnormal laboratory findings or other abnormal safety assessments which are associated with the underlying disease, unless judged by the Investigator to be more severe than expected for the participant’s condition.
- The disease/disorder being studied or expected progression, signs, or symptoms of the disease/disorder being studied, unless more severe than expected for the participant’s condition.
- Medical or surgical procedure (eg, endoscopy, appendectomy): the condition that leads to the procedure is the AE.
- Situations in which an untoward medical occurrence did not occur (social and/or convenience admission to a hospital).

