4 STATISTICAL ANALYSES

4.1 GENERAL CONSIDERATIONS

In general, continuous data will be summarized using the number of observations available, mean, standard deviation (SD), median, minimum, and maximum. Categorical and ordinal data will be summarized using the count and percentage of participants.

The baseline value of efficacy parameters is defined as the last available value before randomization and prior to the first dose of study medication unless below eDiary data (WI-NRS, skin Pain-NRS and Sleep-NRS) score or otherwise specified.

The baseline for weekly average WI-NRS (skin Pain-NRS and Sleep-NRS) score is defined as the average of daily non-missing scores obtained during the 7 days prior to randomization.

The baseline value of the other parameters is defined as the last available value prior to the first dose of investigational medicinal product (IMP) if the participant is treated, or the last available value up to randomization if the participant is not exposed to IMP.

Observation period

The observation period will be divided into 4 segments:

- The **pre-treatment period** is defined as the period up to first IMP administration.
- The **treatment-emergent (TE) period** is defined as the period from the first IMP administration to the last IMP administration + 98 days. The treatment-emergent period includes the following 2 periods:
 - The **on-treatment period** is defined as the period from the first IMP administration to the last administration of the IMP + 14 days
 - The **residual treatment period** is defined as the period from the end of the on-treatment period to the end of the treatment-emergent period.
- The **post-treatment period** is defined as the period from the end of the treatment-emergent period.

The on-study observation period is defined as the time from start of intervention until the end of the study defined as the status date collected on e-CRF page “Completion of End of Study”.

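### Protocol 8.2.1 makes any new or worsened examination finding an adverse event, while 10.3 excludes expected prurigo nodularis, so lesions can enter the TEAE percentage depending on which text a site follows.

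*Protocol*

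**What the plan says.** Protocol 8.2.1 lists the skin, by full-body examination of a disrobed participant, among the systems to be examined, and then says: "Any new finding or worsening of previous finding should be reported as a new AE". The schedule of activities (Section 1.3) places physical examinations at screening, Day 1, Week 24 and Week 36. Participants who stop treatment early have the Week 24 assessments when they stop.

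Section 8.3 says where the definition lies: "The definitions of an AE or SAE can be found in Appendix 3". Under events not meeting the AE definition, Section 10.3 lists "The disease/disorder being studied or expected progression, signs, or symptoms of the disease/disorder being studied, unless more severe than expected" for the participant's condition. It excludes abnormal safety assessments associated with the underlying disease on the same terms. It also says that lack of efficacy is not in itself an AE and belongs to the efficacy assessments. On the other side, Section 10.3 counts as an AE "Exacerbation of a chronic or intermittent pre-existing condition including either an increase in frequency and/or intensity of the condition".

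Two neighbouring rules carry a qualifier that 8.2.1 lacks. Section 7.1.1, on clinically significant findings in general with QTcF as one example, says "Any new clinically relevant finding should be reported as an AE". Section 8.2.4 says of laboratory values: "Clinically significant abnormal laboratory findings are those which are not associated with the underlying disease", again unless more severe than expected.

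The percentage of participants with TEAEs or SAEs through Week 24 is a secondary endpoint (Protocol Sections 3 and 9.4.2). SAP 4.1 defines the treatment-emergent period as the "period from the first IMP administration to the last IMP administration + 98 days". SAP 4.7.2 counts AEs that arise, worsen or become serious in that period. It has no rule for PN terms.

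**The concern.** Inclusion criterion I 04 requires at least 20 PN lesions at screening and on Day 1, so every baseline skin examination has disease findings that can worsen or increase in number. The two sections therefore give opposite answers to a routine question: is a new or worse nodule, within what is expected for this participant, an AE?

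The answer matters because lesions are also an efficacy outcome. Protocol 2.1 states the hypothesis that dupilumab reduces lesions and promotes their healing. If lesions are reported as AEs, fewer would be expected on dupilumab to Week 24, and the TEAE comparison would partly restate efficacy. Blinding does not prevent this, because the treatment effect itself changes how many lesions there are to report. If sites split between the two readings, the count also depends on the site.

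**Working it through.** **The texts side by side**, for a PN lesion that is new or worse at the Week 24 examination:

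| Lesion | Under 8.2.1 | Under 10.3 |
|---|---|---|
| More severe than expected | AE | AE |
| Within expectation | AE | Not an AE |

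The conflict is confined to the second row.

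**Does the examination fall in the treatment-emergent period?** The last planned dose is at Week 22 (Section 1.3) and visits have a window of ±3 days.

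- Last planned dose: 22 × 7 + 1 = Day 155.
- End of the period: 155 + 98 = Day 253.
- Week 24: 24 × 7 + 1 = Day 169, well inside.
- Week 36: 36 × 7 + 1 = Day 253, the last day of the period. A visit on Days 250 to 253 is inside; one on Days 254 to 256 is outside.

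Week 24 carries the point and Week 36 is a boundary case.

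**Possible size.** The plan states no figure that could be reproduced. Let b be the percentage with some other TEAE, equal in both arms; l_P and l_D the percentages with a new or worse lesion on placebo and dupilumab; and f the fraction of those reported as an AE. Assume that lesions are independent of other TEAEs. Then:

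- any-TEAE rate in an arm = b + (1 − b) × l × f
- placebo minus dupilumab = (1 − b) × f × (l_P − l_D)

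Every rate below is assumed; none is in the documents. Differences are in percentage points, placebo higher.

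| b | l_P v l_D | f = 0 (10.3 followed) | f = 0.5 | f = 1 (8.2.1 taken literally) |
|---|---|---|---|---|
| 50% | 10% v 5% | 0 | 1.25 | 2.5 |
| 50% | 20% v 5% | 0 | 3.75 | 7.5 |
| 50% | 30% v 10% | 0 | 5.0 | 10.0 |
| 60% | 10% v 5% | 0 | 1.0 | 2.0 |
| 60% | 20% v 5% | 0 | 3.0 | 6.0 |
| 60% | 30% v 10% | 0 | 4.0 | 8.0 |
| 70% | 10% v 5% | 0 | 0.75 | 1.5 |
| 70% | 20% v 5% | 0 | 2.25 | 4.5 |
| 70% | 30% v 10% | 0 | 3.0 | 6.0 |

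Worked example, b = 60%, lesions 20% v 5%, all reported: placebo 0.60 + 0.40 × 0.20 = 68%; dupilumab 0.60 + 0.40 × 0.05 = 62%. With 75 per arm that is 51 v 46.5 participants.

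**The case against.** The strongest reply is that 10.3 governs. Section 8.3 points to it for the definition and makes investigators responsible for events that meet that definition. Physical examination is one of the safety assessments in Section 8.2, so the exclusion for abnormal safety assessments associated with the underlying disease reaches it directly. Read this way, 8.2.1 is a loosely worded reminder. This stands to a large extent, and many sites would act on it. It does not remove the instruction that applies at the examination itself, which has no cross-reference, and the 10.3 entry on exacerbation of a chronic condition gives a site an honest reason to report.

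It is also fair that the consequence is limited. SAP 4.7 says that safety is descriptive with no testing. TEAEs are tabulated by system organ class and preferred term, so PN-coded events would appear on their own rows. Only the any-TEAE summaries, including the exposure-adjusted rates, would absorb them.

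A reader might infer that findings at both post-baseline examinations always count. They do not. A Week 36 visit after Day 253 is outside the treatment-emergent period, as is the Week 36 visit of a participant who stopped treatment early. The named endpoint ends at Week 24, and data arriving after the primary lock go to an addendum (Protocol 9.6, SAP 4.9). At Week 36 the direction could also reverse, since Protocol 4.2 looks for return of symptoms off treatment.

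A reader might also take 8 to 10 points as the likely effect. That is the upper end of an illustration that assumes both the lesion rates and the reporting of every lesion.

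**Conclusion.** The two sections contradict each other for new or worsened PN lesions of expected severity, and the SAP has no rule that would neutralise the result. Section 10.3 is the likelier governing text, which makes the effect smaller but leaves it to each site's reading. The size cannot be computed from the documents: 0 if all sites follow 10.3, and roughly 1 to 10 points higher on placebo through Week 24 with half to full reporting. That range rests on assumed rates, independence and an equal background in the arms. No hypothesis test, power statement or efficacy result depends on it. The documents do not show that the TEAE comparison is in fact distorted, only that the instructions allow it. The correction is worth making because it is cheap and the endpoint is the main safety summary.

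**What to change.** Reconcile 8.2.1 with 10.3, for example: *Any new or worsened finding that meets the AE definition in Section 10.3 should be reported as an AE.* Send sites a short reminder.

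A change of wording does not recode AEs already collected; the SAP gives 2 January 2020 as the first randomization, and Amendment 03 is dated 21 October 2021. The SAP should therefore state, before database lock, that PN-coded TEAEs are shown separately and that the any-TEAE rate is also given without them. It should name the preferred terms that count as PN. The list in SAP 5.7 was drawn up for medication and procedure indications and includes eczema and infected dermatitis, so it should not be taken over unchanged.

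The cost is a minor amendment, which needs ethics committee approval under Section 10.1.1, a site reminder and one extra table. No new data are needed.

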8.2.2 Vital signs

- Vital signs will be measured in a semi-supine or sitting position after 5 minutes rest and will include body temperature, SBP and DBP, and pulse and respiratory rate. Blood pressure and pulse measurements should be assessed using the same arm with a completely automated device. Manual techniques will be used only if an automated device is not available.
- Body weight (kg) will be measured at screening (Visit 1), EOT, and EOS visits. Height will be measured at screening visit (Visit 1). Height and weight should be measured with indoor clothing but without shoes.

